drink units per day and binge drinking days throughout the trial, which will serve as primary outcome measures.

- *The Penn Alcohol Craving Scale (PACS)*: A self-report paper-and-pencil instrument that assesses various dimensions of craving for alcohol and has been found to have good reliability and validity.⁸¹ The PACS will be administered at baseline and on weeks 8, 13 and 19, and will be used as a primary outcome measure to determine whether prazosin is associated with reductions in alcohol craving.
- *Alcohol Use Disorders Identification Test (AUDIT)*:⁸² A 10-item self-report questionnaire that has served as a screening instrument for alcohol problems in a number of different settings.⁸³ The AUDIT measures at least two factors, one related directly to alcohol consumption and the other to adverse behavioral effects of excessive consumption.^{84, 85} An advantage of the AUDIT is that it can delineate not just individuals likely to have an alcohol use disorder diagnosis but can place respondents on the full spectrum of alcohol misuse from no problem to hazardous drinking to dependence. The AUDIT has well supported reliability, validity, sensitivity, and specificity. The AUDIT will be modified to inquire about the past year, and will be administered at baseline. The AUDIT will be used to characterize the sample.
- *Clinician-Administered PTSD Scale for DSM-IV (CAPS)*:⁸⁶ The 17-item CAPS uses a structured clinical interview designed to assess the 17 symptoms of PTSD outlined in the DSM-IV. The CAPS will be used by the interviewer to make a current (past month DSM-IV diagnoses of PTSD. The frequency and intensity of each symptom on the CAPS is rated on separate 5-point scales, yielding both dichotomous and continuous scores (range = 0 to 8) for each symptom and for the disorder as a whole (range = 0 to 136). The CAPS will be used as a stratification variable for group assignment and as a secondary outcome measure and will be administered at screen, baseline (to be done at baseline only if more than 14 days has elapsed since the screen visit) and weeks 8, 13 and 19.
- *Pittsburgh Sleep Quality Index (PSQI)*⁸⁷: A self-report questionnaire assessing sleep quality and disturbances over a 1-month time interval. Nineteen individual items generate seven subscale scores: subjective sleep quality, sleep latency, sleep duration, habitual sleep efficiency, sleep disturbances, use of sleeping medication, and daytime dysfunction. A global score may be obtained by summing the seven component subscales (total score range: 0-21). The PSQI will be used as a secondary outcome measure and will be completed at baseline and weeks 8, 13 and 19.
- *Short Inventory of Problems (SIP)*:⁸⁸ This 15-item self-report questionnaire will be used to assess problems with alcohol, other than alcohol dependence. The SIP has been found to have adequate test-retest reliability and internal consistency. The SIP will be used as a secondary outcome measure to determine whether prazosin is associated with reductions in alcohol-related problems. This self-report instrument will be completed at baseline and weeks 8, 13 and 19.
- *PTSD Checklist-Military (PCL-Military)*:⁸⁹ A well validated 17-item self-report measure assessing severity of PTSD symptoms specifically in the military combat operations context consistent with DSM-IV criteria, with scores ranging from 17 to 85. The PCL-M will be completed at baseline and weeks 8, 13 and 19.
- *Patient Health Questionnaire-9 (PHQ-9)*:⁹⁰ The 9-item depression module of the Patient Health Questionnaire, a self-report version of the PRIME-MD used to diagnose major mental disorders. The PHQ-9 items correspond with DSM-IV criteria for depression, with each item scored from "not at all" to "nearly every day." Items of the PHQ-9 are internally consistent (alpha = 0.86-0.89) and the questionnaire exhibits high test-retest reliability coefficients. Agreement between the PHQ-9 and clinician-based interview diagnosis of major depression is high, with a sensitivity of 88% and a specificity of 88% using a PHQ-9 score ≥ 10 . The PHQ-9 will be completed at baseline and weeks 8, 13 and 19.
- *Family History of Drinking Problems*:⁹⁴ A study staff administered instrument to collect information regarding family history of alcohol use. The instrument does not identify family members beyond labeling titles of mother, father and siblings 1 through 10. In a study of the prazosin-like alpha-1 adrenoreceptor antagonist doxazosin, a positive family history predicted a positive response to doxazosin. This information may be helpful in predicting which patients may have a positive response to prazosin.

10.3 At any point in the study, will you request, use, or access data from a DoD Database or the Military Health System (MHS)?

Yes No

10.4 Review the definitions below and respond to the following two questions. If you are not sure of the answers, email [contact] for assistance.

The Military Health System (MHS) is defined as all DoD health plans and DoD health care providers that are organized under the management authority of, or in the case of covered individual providers, assigned to or employed by, the Defense Health Agency (DHA), the Army, the Navy, or the Air Force

MHS workforce members are employees, volunteers, trainees, and other persons whose conduct, in the performance of work for the MHS, is under the direct control of the MHS, whether or not they are paid by the MHS.

MHS business associates are persons or entities that provide a service to the MHS and require protected health information (PHI) to provide the service.

Are you an MHS workforce member?

Yes, I am an MHS workforce member
 No, I am not an MHS workforce member

Are you an MHS business associate?

Yes, I am an MHS business associate
 No, I am not an MHS business associate

10.5 Have you consulted with an MHS data expert to determine the data elements required for your study?

Consulting with a data expert often saves time later in the compliance process because the data expert can advise on the data available in the numerous MHS information systems, the quality of that data and the methods for encrypting and collapsing data. To schedule a consult with an MHS data expert, send an email to: **([contact])**

Yes, then complete the questions below according to the data consult
 No, then complete the questions below according to the best of your knowledge

10.6 Indicate how you will request data from the MHS. Select all that apply.

Talking with MHS health care providers or MHS health plans about specific research participants
 Obtaining MHS hard copy records specific to research participants
 Obtaining data from an MHS information system(s)

10.7 If you are obtaining data from an MHS information system(s), indicate whether you plan to receive a data extract or whether you plan to access an MHS information system directly to create a data set.

A data extract is when the MHS or a contractor provides the data set directly to the researcher. When receiving a data set through data extract, the researcher may indicate whether the data elements should be provided as is, encrypted or collapsed. In contrast to a data extract, access to an information system means that the researcher may directly access an MHS information system and create a data set for the research study

Data Extract

Access

10.8 Do you intend to use only de-identified data from the MHS in your research study?

There are different two methods for de-identifying data pursuant to HIPAA:

- 1) Safe Harbor Method: Removing all of the identifiers listed in Table 1 below, provided that the researcher does not have actual knowledge that the remaining data can be used alone or in combination with other information to identify the individual who is the subject of the information
- 2) Statistical Method: An expert, with appropriate knowledge of and experience with generally accepted statistical and scientific principles and methods for rendering information not individually identifiable, determines that the data is not individually identifiable

Yes No

10.9 Indicate the MHS information system(s) from which you will seek to obtain data

If you do not know which system(s) contains the data elements you need, refer to the Guide for DoD Researchers on Using MHS Data or request guidance from an MHS data expert at: **DHA**.

[contact].

Below is a list of commonly used MHS systems. If the system from which you seek to obtain data is not listed below, list the name of the system in the "Other MHS Systems" category below

PHI Systems:

MHS Information System	Requesting Data
:AHLTA	:Yes
:ESSENTRIS	:Yes

PII-Only Systems:

MHS Information System	Requesting Data
MHS Genesis	:Yes

Information System	Requesting Data
No records have been added	

10.10 Do you intend to merge or otherwise associate the requested data with data from any sources outside of the MHS, including other DoD systems that are not part of the MHS?

Yes, will merge data
 No, will not merge data

10.11 Indicate the data elements about research participants or relatives, employers, or household members of the research participants that you will request from MHS hard copies or from MHS information systems.

If you answered "yes" to question 10.9 above, also indicate non-MHS data elements about research participants or relatives, employers, or household members of the research participants that you will have access to in any form or medium.

Data Element(s)	MHS	Non-MHS Systems	MHS Hard Copies
1. Names			

2. Postal address with only town, city, state and zip code				
3. Postal address with all geographic subdivisions smaller than a state, including street address, city, county, precinct, zip code and their equivalent geocodes, except for the initial three digits of a zip code if, according to the current publicly available data from the Bureau of Census: 1) the geographic unit formed by combining all zip codes with the same three initial digits contains more than 20,000 people; and 2) the initial three digits of a zip code for all such geographic units containing 20,000 or fewer people is changed to 000				
4. Dates including all elements (except year) directly related to an individual, including birth date, admission date, discharge date, and date of death				
5. Ages over 89 and all elements of dates (including year) indicative of such age, unless you will only request a single category of "age 90 or older"				
6. Telephone numbers				
7. Fax numbers				
8. Electronic mail addresses				
9. Social Security numbers (SSNs)				
10. Medical record numbers				

11. Health plan beneficiary numbers				
12. Account numbers				
13. Certificate/license numbers				
14. Vehicle identifiers and serial numbers, including license plate numbers				
15. Device identifiers and serial numbers				
16. Web Universal Resource Locators (URLs)				
17. Internet Protocol (IP) address numbers				
18. Biometric identifiers, including finger and voice prints				
19. Full-face photographic images and any comparable images				
20. Any other unique identifying number, characteristic, or code (DEERs ID, EDIPN, Rank)				

If you are obtaining SSNs, provide a justification as to why and explain why a substitute cannot be used

The study will use social security numbers to abstract data from electronic health records.

10.12 Do you believe it is possible for the MHS data to become identifiable because of triangulation, a small cell size, or any unique data element(s)?

Triangulation means using different data elements that are not themselves identifiable but that when combined can be used to identify an individual. For example, triangulation would use rank and race together to determine the identity of an individual with a particular health condition.

Small cell size means that there is only a small number of eligible individuals that satisfy the category description. Guidance for acceptable cell size is available from the Centers for Medicare and Medicaid Services. For example, the rank category of four star generals with a particular diagnosis may be less than 30, so the rank category may need to be expanded to include lower ranks.

A unique data element includes any unique features that are not explicitly enumerated in the categories of data in rows 1 – 20 of the table above (in Section 10.10), but that could be used to identify an individual. Unique data elements include characteristics that are not themselves identifying, such as the

rank of general or admiral, or a race or gender, but within the context of other information could be identifiable.

- Yes, I believe there is a reasonable possibility the MHS data will become identifiable
- No, I believe there is no reasonable possibility the MHS data will become identifiable

10.13 HIPAA Privacy Rule and Use of Protected Health Information in Research:

- N/A – will not use or disclose protected health information (PHI)
- HIPAA Authorization will be obtained
- Use of a limited data set where a data use agreement will be obtained
- Waiver/alteration of HIPAA Authorization is being requested

10.14 Managing Data (Data Management and/or Sharing Plan) and/or Human Biological Specimens for this Study:

Include in this section the plan for acquiring data (both electronic and hard copy), access during the study, data/specimen storage and length of time stored, shipment/transmission, and the plan for storage and final disposition at the conclusion of the study. Describe any data agreements in place for accessing data within and/or outside of your institution (e.g., Data Sharing Agreement, Data Use Agreement, Business Agreements, etc.)

Study personnel will have access to participants' medical records during the period of study participation and for 30 days after study completion or early discontinuation. Records will be reviewed to monitor for changes in health, adverse events, any laboratory results, and completion status of the treatment program. Laboratory results may include urine toxicology screens performed as part of the participant's treatment. Other than the labs listed as being done at screening visit and the GGT that will be obtained at baseline and weeks 8, 13, and 19, no clinical labs will be done as part of the study.

Approximately 7 ml of blood will be drawn for liver function tests (AST, ALT) at the screen visit. Other clinical labs (chemistry panel, and complete blood count) at the screen visit, if clinically indicated. If the additional labs are drawn, a total of 15 ml of blood will be drawn at the screen visit. Urine will be collected at the screen visit for routine urinalysis, if clinically indicated. A urine sample for urine pregnancy test will also be collected at the screening visit from women of childbearing potential.

Blood samples (approx. 10 ml each) will be collected at baseline and at weeks 8, 13 and 19 for PEth and GGT measurement.

All samples will be used in their entirety for the testing specified. No samples will be stored for future research.

All information collected at study visits will be recorded on standardized case report forms. Forms will be labeled with study code number only. Code numbers will be assigned sequentially and will not include participant initials or any other identifiers. Case report forms (coded without identifying information) will be stored on shelves in a locked room in the VA Puget Sound Mental Illness Research and Education Center (MIRECC) offices. The CRFs are needed at VA Puget Sound because the data from the CRFs is entered by VA Puget Sound staff and because VA Puget Sound is the study coordinating center.

Source documents (research charts, which may contain identifying information) will be maintained in locked cabinets within a locked room at VA Puget Sound in the MIRECC offices. (Offices are currently located at the Seattle division in Building 1, Rooms B22 and B25.) Only those people on the approved protocol will have access to the secured documents. Research charts must be stored at VA Puget Sound because the bulk of the study staff are located at VA Puget Sound. Participants are asked to call the medical providers at VA Puget Sound if they have an adverse event, and are instructed to call the study coordinators at VA Puget Sound if they need to cancel or reschedule an appointment.

Providers for this study are located in offices at JBLM, Madigan clinics, and VA Puget Sound. If at any time access to a research chart that is stored at VA Puget Sound is required, such information may be faxed to the PI. The study team will meet on a weekly basis to discuss study participants and any study concerns ensuring the PI is continually informed regarding all current participants.

All documents will be stored in compliance with record storage policies at VA Puget Sound. The files will be hand carried in locked boxes or containers between JBLM and VA Puget Sound in a HIPAA-compliant secured container and will only be accessible to the persons named on the protocol. The Database Manager will provide database design and maintenance and any required computer programming. VA Puget Sound and the VA Northwest Network MIRECC will provide maintenance of computer hardware and software at VA Puget Sound. Initial and second data entry will be performed regularly at VA Puget Sound by a Research Assistant under the supervision of the Database Manager. The Database Manager will

generate reports of data discrepancies. The Research Assistant under the supervision of the Study Coordinator and Data Manager will be responsible for rectifying data entry errors on a regular basis. Data will be analyzed using Statistical Package for Social Sciences (SPSS) software. Database maintenance includes nightly backup of hard drives and storage of backups at a secure location off-site. Only personnel having the correct user name, password, and signing on from a computer with the appropriate IP address will have access to the database.

Disposition of Data: Case report forms will be stored indefinitely in a locked room accessible only to MIRECC investigators and staff at VA Puget Sound, Seattle division (currently Building 1, Rooms B22 and B25). The Data Managers and Biostatistician will not have access to the link between study code numbers and participant identities. The Project Leader and Study Coordinator will maintain the password-protected link between study code numbers and participant identities. This document will be stored on the VA Research server in a workgroup that is only accessible to approved personnel. The VA Research server is FIPS 140-2 compliant.

Because a Records Retention Schedule approved by National Archives and Records Administration is required to destroy Federal records, and because at this time there is not such a schedule for VA research records, we must retain data pending approval of such a schedule. Therefore, all study data, including the link between participant identities and study code numbers will be maintained until we have permission to destroy them or until data analysis is complete (whichever comes later).

At that time, the code list will be destroyed in compliance with Federal Guidelines in force when the records are destroyed (currently outlined in 44 USC3302§1228.5). The electronic code list will be destroyed in compliance with Federal Guidelines (Currently national Archives and Records Administration rules and National Institute of Standards and Technology 800-88 guidelines for Media Sanitization) and all study data will become anonymous. Anonymous study data will be kept indefinitely.

10.15 Managing Data (Data Management and/or Sharing Plan) and/or Human Biological Specimens for Future Research:

If the study involves collecting, storing, or banking human specimens, data, or documents (either by the Investigator or through an established repository) for FUTURE research, address. How the specimens /data will be used, where and how data/specimens will be stored (including shipping procedures, storage plan, etc.), whether and how consent will be obtained, procedures that will fulfill subjects' request as stated in the consent, whether subjects may withdraw their data/specimens from storage, whether and how subjects may be recontacted for future research and given the option to decline, whether there will be genetic testing on the specimens, who will have access to the data/specimens, and the linkage, the length of time that data/specimens will be stored and conditions under which data/specimens will be destroyed.

This study does not bank data or specimens for future research.

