Study weeks 0-2 —Study Drug Titration: Following completion of baseline assessments, participants will be randomized 1:1 to prazosin or placebo. The initial dose will be 1 mg prazosin or placebo capsule taken at bedtime for 2 nights. The first dose of prazosin/placebo will be taken while the participant is in bed for the night to avoid orthostatic syncope, an uncommon but recognized “first dose” effect of prazosin or any alpha-1 antagonist if started at a high dose. The first dose effect is avoidable by starting treatment with a low dose (1 mg before bedtime) and then titrating the dose upward gradually. Such titration avoids excessive blood pressure reduction.

The participant will be asked to call the study team the morning after the first dose to make sure there was no occurrence of postural dizziness. If there have not been any adverse events, the participant will be instructed to increase the dose to 1 mg three times per day (morning, afternoon and bedtime) on the third day. The participant will be given 24-hour contact number in case of adverse events when the dose is increased. However, in our prior study of prazosin in AUD, there has been no problem with this dose increase.

Participants will undergo 2 additional titration visits (weeks 1 and 2). At each titration visit, seated /supine and standing BP and HR will be measured, and presence of side effects and/or adverse events will be assessed. Concomitant medications and health status will be updated. The alcohol use calendar will be administered at every study visit. P

Mid-week titration increases will occur if the participant does not experience any unacceptable side effects. A 24-hour contact number will be provided should any adverse events occur at any time.

A dose increase will occur if the participant does NOT have unacceptable side effects. Clinical judgement may be used to maintain or decrease the dose as necessary. If the participant has intolerable side effects during the titration period, the dose will be reduced to the previous titration step. The dose may be re-challenged if clinically appropriate.

Titration will proceed according to the following schedule:

Study Drug Dose Schedule

		AM	MIDDAY	BEDTIME
Week 0/BL	Days 1-2			1 mg
	Days 3-4	1 mg	1 mg	1 mg
	Days 5-7	2 mg	2 mg	2 mg
Week 1	Days 8-10	2 mg	2 mg	6 mg
	Days 11-14	4 mg	4 mg	6 mg
Week 2	Days 15-21	4 mg	4 mg	8 mg
Week 3	Days 22-end of study	4 mg	6 mg	10 mg

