The titration schedule and target dose were chosen based on clinical experience in treating PTSD with prazosin and on our initial study for AUD in which this titration schedule was well tolerated.¹⁵ Typical, effective, and well-tolerated doses of prazosin in Veterans with PTSD treated at VA Puget Sound range between 5-30 mg/day.⁷⁷ In our prior work with prazosin, study participants have tolerated without difficulty abrupt discontinuation of these doses of prazosin with no need for tapered withdrawal.

Weeks 3-5: If participants delay titration for any reason (e.g., dose maintained and not increased due to temporary AE), the dose may be increased/adjusted through week 5. No dose changes will be allowed after week 5. If titration is required, procedures noted for weeks 1-2 (above) will be followed. If no titration is required, procedures for weeks 6-13 (below) will be followed.

Weeks 6-13: Participants will be asked to return at weeks 6, 7, 8, 9, 11, and 13. At each visit, vital signs, including orthostatic BP and HR, will be measured. Side effects and/or adverse events (if any) will be monitored by open-ended AE reporting and the Adverse Symptom Checklist which includes symptoms which may be attributable to prazosin (e.g., lightheadedness, dizziness on standing, palpitations, drowsiness, headache, nausea, lack of energy, weakness, depressed mood). For vital signs parameters, hypotension will be defined as systolic BP < 90 and clinically meaningful orthostatic hypotension defined as ≥ 20 mmHg drop in systolic BP accompanied by lightheadedness or syncope. If the participant develops an unacceptable adverse effect considered related to study drug, downward dose adjustment will be made.

Concomitant medications and health status will be updated.

The alcohol use calendar will be administered at every study visit. Outcome assessments (CAPS, PCL-M, PHQ-9, PACS, SIP, PSQI) will be administered at weeks 8 and 13.

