Study Discontinuation or Termination: If the participant is not able to tolerate a minimum dose of 3 mg /day of placebo/prazosin, he or she will undergo early termination and all week 13 assessments will be performed; the participant will be referred to his/her primary mental health care provider for further management. Reasons for early discontinuation or withdrawal will be recorded.

Participants may be discontinued prematurely from study treatment to manage deterioration of clinical status. Specifically, dangerousness toward self or others or emergence of acute psychiatric symptoms necessitating hospitalization will result in discontinuation from the study. If at any time during the study, psychiatric symptoms become markedly increased resulting in severe participant distress or presenting immediate danger to self or others, the participant will be discontinued from the study. In case of need for increased level of care or emergent care, study personnel will provide a warm hand-off to DBH personnel. DBH personnel will assume responsibility for arranging appropriate care.

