Prazosin may cause syncope. In most cases this is believed to be due to excessive postural hypotension although occasionally the syncopal episode has been preceded by severe tachycardia with heart rates of 120-180 beats per minute. Syncopal episodes have usually occurred within 30-90 minutes of the initial dose. The incidence of the syncopal episodes is 1% if the initial dose is 2 mg or more. Clinical trials suggest that syncopal episodes can be minimized by starting with a dose of 1 mg and slowly titrating up to the final dose, as we are doing in this study.

In post-marketing experience, Intraoperative Floppy Iris Syndrome (IFIS) has been observed during cataract surgery in some patients who are taking or have taken alpha-1 blockers. The patient's ophthalmologist should be prepared for possible modifications to the surgical technique to reduce the surgical risk of IFIS. If a patient needs to have cataract surgery, he/she should tell his/her eye surgeon that he/she may have taken prazosin in a research study.

Prazosin should not be taken concurrently with trazodone. Potential participants who are taking trazodone for sleep and who are willing to discontinue will be washed out before starting this study. Care should be taken when alpha-1 blockers are combined with erectile dysfunction medications. We will be following VA pharmacy prescribing guidelines regarding these medications. Erectile dysfunction medications will not be allowed during the titration period. Once stable dose has been reached, participants will be allowed to use ED drugs at half the usual clinical dose.

Participants will be monitored at each visit for adverse events. Any adverse event will be managed by the study team as clinically appropriate. If necessary, a participant will be referred for treatment of an adverse event. Adverse event reporting will begin after the dispensing of the first dose of study drug. All events reported prior to dispensing of the first dose of study drug shall be part of the participant's health history.

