Women of childbearing potential must have a negative urine pregnancy test at screen and within one week of starting study drug. Female participants must agree to abstain from sexual relations that could result in pregnancy or use an effective method of birth control acceptable to both participant and the study clinician during the study in order to be eligible. Women who are nursing will not be eligible for study participation. Any woman who becomes pregnant during the course of the study will be discontinued from the study but will continue with customary AUD treatment or treatment with her DBH provider.

Risks of medication side effects will be minimized by starting at a low dose and titrating up to the maximum dose over a period of weeks, by maintaining frequent contact with study participants, and by performing safety assessments on a regular schedule. As a further precaution, male participants will be advised to sit on the toilet for urination during the first week of dose titration.

Vital signs, including orthostatic BP and HR, will be performed at all in-person study visits. Systolic and diastolic BP and HR will be obtained following at least 10 minutes of seated/supine posture and then repeated following 2 minutes of standing. Occurrence of lightheadedness, dizziness on standing, palpitations, drowsiness, headache, nausea, nasal congestion, peripheral edema, and other adverse effects will be rated by a study clinician. For vital signs parameters, unacceptable side effects will include seated/supine hypotension (seated/supine systolic BP < 90) and clinically meaningful orthostatic hypotension (≥ 20 mmHg drop in systolic BP accompanied by lightheadedness or syncope).

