Safety procedures specific to the war zone trauma population: Participants will be discontinued from the study to manage marked deterioration of clinical status or if the study clinician determines the participant is not stable enough to continue participation. For example, psychiatric symptoms become markedly increased resulting in severe participant distress, dangerousness toward self or others or emergence of acute psychiatric symptoms necessitating hospitalization. Study termination will be followed by a warm hand-off to DBH personnel. DBH personnel will assume responsibility for arranging appropriate care. A study clinician will be on call at all times to receive telephone calls from participants regarding any adverse events; participants will be provided with a 24-hour emergency contact number.

Participants are asked about suicidal ideation at each visit. If endorsed, participants will be assessed as to their level of risk and the level of care required to keep themselves or others from harm. If a participant requires inpatient treatment in order to prevent harm or is found to have symptoms of disorganized thought processes secondary to psychosis, DBH personnel will be notified immediately to assist with appropriate triage and referral.

Protection against risk of loss of confidentiality: Confidentiality is strict. All case report forms (CRFs) will be stored by participant code and no identifying information will be included with CRFs. Study records and data will be kept in a secure location as described below or on restricted-access, password-protected servers. Identifiable information will not be stored with study data. Only the persons named on the Madigan and VA Puget Sound IRB applications will have access to the source documents and original research data. Data will not be revealed to insurance companies or other individuals or organizations.

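### The protocol bars every dose change after week 5, yet requires a dose reduction for unacceptable drug-related effects in weeks 6-13; the bar should be limited to increases

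*Combined protocol and SAP*

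**What the plan says.** The dosing rules are in section 10.1 (Study Procedures), arranged by study week.

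- **Weeks 0-2 (titration).** Steps up depend on tolerability, and "Clinical judgement may be used to maintain or decrease the dose as necessary".
- **Weeks 3-5.** This paragraph covers participants whose titration was delayed. For them "the dose may be increased/adjusted through week 5", and then "No dose changes will be allowed after week 5".
- **Weeks 6-13.** This paragraph defines hypotension and then states: "If the participant develops an unacceptable adverse effect considered related to study drug, downward dose adjustment will be made".

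Three later sections bear on the same situation. Section 14.2 says that "unacceptable side effects will include seated/supine hypotension (seated/supine systolic BP < 90) and clinically meaningful orthostatic hypotension". Section 13.6 gives a floor for early termination, with no week limit: "If the participant is not able to tolerate a minimum dose of 3 mg" per day. Section 14.1 adds a general provision: "Any adverse event will be managed by the study team as clinically appropriate".

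**The concern.** A downward adjustment is a dose change. The Weeks 3-5 sentence has no exception for safety, and the Weeks 6-13 sentence is mandatory. Neither refers to the other. A member of staff who meets a hypotensive participant after week 5 therefore has two current instructions that cannot both be obeyed.

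What is at stake is the clarity of a safety procedure. Taken alone, the bar would keep a participant at full dose with a blood pressure that the protocol itself calls unacceptable, or leave discontinuation as the alternative. Dose orders are written by the team and filled against a label by the investigational pharmacy, so all parties need the same rule.

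**Working it through.** No sample size, power or error-rate figure is involved, so the check compares the text.

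1. **Does the bar cover reductions?** The sentence speaks of changes, not increases. The sentence before it allows the dose to be increased or adjusted through week 5, so the drafters had movement in both directions in view. The wording does not limit the bar to up-titration.

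2. **Does anything else point to a fixed dose?** Yes. Section 10.1 describes ten weeks on a stable dose, and the last row of the dose schedule runs from day 22 to the end of the study at 4 + 6 + 10 = 20 mg/day. Neither text mentions late reductions.

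3. **Is the trigger for a reduction defined and measured?** Yes. Section 14.2 names the blood-pressure criteria that count as unacceptable and has orthostatic vital signs taken at every in-person visit. After week 5, visits at weeks 6, 7, 8, 9 and 11 fall before study drug ends at week 13.

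4. **Illustrative case.** A participant on 20 mg/day has a seated systolic pressure of 86 at week 7, judged related to study drug. Since 86 is below 90, the effect is unacceptable under section 14.2. The Weeks 3-5 sentence says to keep 20 mg/day. The Weeks 6-13 sentence says to lower it.

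5. **Does any other text settle the order of precedence?** No.
   - The clinical-judgement provision belongs to the titration paragraphs and does not say that it continues after week 5.
   - The 3 mg/day floor in section 13.6 has no week limit, which suits a protocol that expects reductions, but it governs termination only.
   - Section 14.1 allows clinically appropriate management without mentioning dose.
   - Section 14.2 allows discontinuation "if the study clinician determines the participant is not stable enough to continue participation", which is a different remedy.

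6. **Does the conflict reach the analysis?** No. The primary analysis in section 11.1 is by intention to treat, so a dose reduction removes nobody from it. The power statement in section 11.2 uses drinking and craving data with 60 per group and has no input for late dose changes.

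The contradiction is therefore real on the page, and its practical frequency is unknown.

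**The case against.** The strongest reply is that the protocol resolves the matter itself. The bar closes a paragraph about delayed titration, so its natural purpose is to end the titration window. The disputed period has its own paragraph, which comes later, is more specific and is mandatory. A clinician at week 7 would turn to the Weeks 6-13 procedures and lower the dose. Sections 13.6, 14.1 and 14.2 all point the same way.

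Most of this stands. It shows the probable intent and keeps the practical risk small. It does not remove the fault, because the exception is nowhere written and the bar is categorical in current operative text.

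A reader might infer that participants would in fact be held at a hypotensive dose. The documents do not support that, given the mandatory Weeks 6-13 rule and the other routes for managing adverse events.

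A reader might also infer that a safety reduction puts someone off protocol and so distorts the completers analysis in section 11.1. That does not follow either. The reduction is itself a protocol instruction. Section 11.1 does not define staying on protocol by dose, and section 11.6 defines completion by attendance.

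**Conclusion.** The point holds as a contradiction in wording within a safety procedure. One sentence forbids what the next paragraph requires. It should be corrected, but its size is modest: one sentence is wrong, probable practice already follows the safer rule, and the intention-to-treat analysis, power and sample size do not change.

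The documents give no rate of late dose reductions, so neither the number of participants affected nor any effect on results can be derived. The number of weeks that the bar spans would show only how long the sentence applies, not how much harm it does.

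The conclusion rests on reading the bar as written. The view that practical risk is small rests on the assumption that clinicians give precedence to the later, more specific rule.

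**What to change.** In section 10.1, Weeks 3-5, replace the sentence that bars dose changes with:

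*No dose increase, including re-escalation, is allowed after week 5. Downward adjustment for an unacceptable adverse effect judged related to study drug will be made at any week, as described under Weeks 6-13.*

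Leave the Weeks 6-13 sentence unchanged. The replacement must keep two of its features: the reduction is mandatory, so it should not be made a matter of clinical judgement, and it applies to effects attributed to study drug. Naming re-escalation settles whether a lowered dose can be raised again after week 5.

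Section 11.1 needs no addition. A statement that anyone with a reduced dose stays in the completers analysis would, read literally, retain a participant who later drops out.

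Optionally, add the seated or supine posture to the systolic threshold in the Weeks 6-13 paragraph, to match section 14.2. This is editorial only.

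The cost is one replaced sentence in a protocol amendment. No visit, measurement or analysis is added, because the blood pressures are already taken at each in-person visit.
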